8.2 Analyses of Secondary outcomes

8.2.1 Other measures of neurodevelopmental outcome

A per-protocol analysis of the mean difference of the Cognitive component of the Bayley III scale between arms adjusted for gestational age will be presented with a 2-sided 95% confidence interval. Equivalence will be accepted if the confidence interval of the difference in means lies within -5 and +5 points.

For other continuous data, groups will be compared as for the primary outcome with the gestation-adjusted mean difference in scores presented with a 2-sided 95% confidence interval. For frequency data difference in frequency between groups will be presented with a 2-sided 95% confidence interval.

8.2.2 Apnoea:

There will be four Apnoea outcomes.

- Early significant apnoea on vital signs
- Late significant apnoea on vital signs
- Intervention for early apnoea
- Intervention for late apnoea

For each apnoea outcome an adjusted regression analysis will be performed to assess associations between risk factors and apnoea.

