Due to the difficulties with cohort data, the best way to provide convincing evidence for the safety of volatile anaesthesia is with a prospective randomised trial. Fortuitously, in many sites, anaesthesia is provided to infants undergoing inguinal hernia repair via one of two methods – general anaesthesia (GA) or regional anaesthesia (RA). RA can be with spinal or caudal anaesthesia or a combination of both. RA can be provided without exposure to any of the agents purported to be associated with neuro-toxicity. Inguinal hernia repair is one of the most common procedures to be performed in infancy and provides a large population of infants having similar surgery. The reasons for choosing RA or GA may depend on the age of the child, the experience of the surgeon or anaesthetist, and the perceived risk of apnoea. As outlined below the risks of apnoea after modern anaesthesia are not clearly defined. The presence of equipoise in choice of anaesthesia for a single, relatively common procedure provides an ideal setting for a prospective randomised trial. The most important potentially confounding variable is the influence of prematurity on developmental outcome and choice of anaesthesia. This potentially confounding variable makes stratified randomisation and a subsequent stratified analysis essential.

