3. STUDY DESIGN

3.1 Experimental Design: Prospective, observer blind, multi-site, randomised, controlled, equivalence trial

3.2 Randomisation: Randomisation to either of the two treatment groups (GA or RA) will be by block and stratified by site and gestational age at birth. Gestational age at birth strata will be:

- 26 weeks to 29 weeks and 6 days
- 30 weeks to 36 weeks and 6 days
- 37 weeks and more

Access to randomisation numbers will be via a 24 hour web-based randomisation service set up and maintained by A/[name] at The Data Management & Analysis Centre, Department of Public Health, University of Adelaide, South Australia: http://www.dmac.adelaide.edu.au/gasRandomisation

Entry to the website is password protected.

3.3 Blinding: The anaesthetist will be aware of the group allocation. The psychologist and paediatrician performing the 2 and 5 year neurodevelopmental assessments will be blinded to study group. Parents will not be told which group their child was in but they will be allowed to discover the group and will be told if asked. Parents will be clearly instructed that if they do discover the group then they should not inform the assessing psychologist. A record will be made of whether or not the parents or the psychologist became aware of the allocation. The apnoea assessment and recovery assessment will not be blinded.

3.4 Study duration: The duration of subject participation is five years.

- Children will be enrolled before surgery.
- Data will be collected before and during anaesthesia and in the early postoperative period.
- Formal neurodevelopmental assessment will occur at 2 and 5 years corrected age (see appendix 1 for definition of corrected age).

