8. STATISTICAL CONSIDERATIONS

8.1 Analysis of primary outcome

Since this an equivalence study, the primary outcome will be analysed on a perprotocol analysis basis to ensure a conservative estimate in the direction of nonequivalence. The means will be adjusted for gestational age at birth. The adjusted mean difference in Full Scale IQ Score between arms will be presented with a 2-sided 95% confidence interval. Equivalence will be accepted if the confidence interval of the difference in means lies within -5 and +5 points.

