8.3 Justification of numbers

The WPPSI-III full scale IQ score is a standardised score with a mean of 100 and standard deviation of 15. Cohort studies of ex-preterm babies at 5 years of age commonly show a mean of 95 and standard deviation of 15, while term babies have a mean of approximately 105 and a standard deviation of 15. A difference of 5 points (1/3 of a standard deviation) will be taken as the largest difference that would be acceptable to demonstrate equivalence.

The sample size is calculated using the two one-sided equivalence tests method (ref: Schuirmann, D.J.) with a one-sided alpha of 0.025, applied to the null hypothesis that the two methods of anaesthesia are not equivalent, and power of 90% under the alternative hypothesis that the true mean difference is one standardised score point. Restated, we require 90% probability that the 95% confidence interval for the difference in means, adjusted for gestational age at birth, will exclude a difference of 5 or more (i.e. the 95% CI will lie within the range -5 to +5), if the true difference is no more than one point. The trial then needs 598 infants in total. Enrolling 660 will allow for an average of 10% loss to follow-up.

Adjusting the analysis for gestational age at birth, according to the three categories used in the stratified randomization, will ensure that the common standard deviation assumption is protected from the differences in WPPSI-III full scale IQ mean scores between the gestational age groups. Simulations have been performed to confirm these calculations.

Reference

Schuirmann, D.J. A comparison of the two one-sided tests procedure and the power approach for assessing the equivalence of average bioavailability. Journal of Pharmacokinetics and Biopharmaceutics 15(1987) pp. 657-680

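### Section 8.2.1 adjusts the continuous neurodevelopmental scores for gestational age but gives binary outcomes a plain difference in frequency, at odds with the stratified analysis that section 1.4.2 calls for (minor)

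*Protocol*

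**What the plan says.** - **Section 1.4.2, last paragraph**, names prematurity as the chief potential confounder, through its influence on development and on the choice of anaesthetic, and concludes: "This potentially confounding variable makes stratified randomisation and a subsequent stratified analysis essential".
- **Section 3.2**: randomisation "will be by block and stratified by site and gestational age at birth", with three gestational-age bands.
- **Section 8.1**, on the IQ score: "The means will be adjusted for gestational age at birth". On the analysis set: "the primary outcome will be analysed on a perprotocol analysis basis".
- **Section 8.2.1** adjusts the Bayley cognitive score for gestational age, again per protocol, and continues: "For other continuous data, groups will be compared as for the primary outcome with the gestation-adjusted mean difference in scores". The following sentence is "For frequency data difference in frequency between groups will be presented with a 2-sided 95% confidence interval". It names neither an adjustment nor an analysis population.
- **Section 8.2.2** treats apnoea, also a frequency outcome, separately: "For each apnoea outcome an adjusted regression analysis will be performed to assess associations between risk factors and apnoea".
- **Section 8.3** gives a reason for adjusting that is specific to IQ: doing so "will ensure that the common standard deviation assumption is protected from the differences in WPPSI-III full scale IQ mean scores".
- **Section 6.2.1** lists what the frequency sentence would cover: presence of cerebral palsy at 2 years, with the same paediatric assessment at 5 years, and data on visual and hearing acuity.

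**The concern.** Two adjacent sentences of 8.2.1 treat two kinds of neurodevelopmental outcome differently, and no reason is given. The argument in 1.4.2 concerns developmental outcome in general, so it applies to cerebral palsy as much as to a test score. An analyst who follows 8.2.1 literally would program a crude difference and ignore a factor used in the randomisation.

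Two things are at stake. First, an interval that ignores a prognostic stratification factor is somewhat wider than it need be. Second, stratified randomisation balances gestation only among the infants randomised. Conversion from regional to general anaesthesia (section 5.7) can occur in the regional arm only. If frequency data were analysed per protocol, or if follow-up were lost unevenly, the gestational mix of the arms could drift apart, and a crude difference would absorb that drift.

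**Working it through.** **Inputs from the protocol.** No figure is stated for any frequency outcome. The only sample-size figure is 598 evaluable infants for IQ (8.3). It reproduces: two one-sided tests at 0.025, SD 15, margin 5 and true difference 1 give power 0.9007 at 299 per arm and 0.8997 at 298. Enrolling 660 with 10% loss leaves 660 × 0.90 = 594, or 297 per arm with 1:1 allocation (assumed, as no ratio is stated).

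**Assumed inputs.** The protocol gives no band shares *w*, event risks *p* or band-specific losses *f*. They are varied below, in the order 26–29, 30–36 and 37+ weeks.

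**Formulas**, with no true effect and n = 297 per arm:
- overall risk P = Σ w·p
- crude SE = √(2·P(1−P)/n)
- stratified SE = √(2·Σ w·p(1−p)/n)
- if the regional arm alone loses fractions f, its shares become w(1−f)/Σw(1−f), and the crude difference (general minus regional) becomes P minus the regional risk under the new shares.

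**Precision, all randomised infants compared**

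| Scenario | Shares | Risks | P | Crude SE (points) | Stratified SE (points) | Crude SE larger by |
|---|---|---|---|---|---|---|
| A | 20/40/40% | 10/4/1% | 4.0% | 1.608 | 1.585 | 1.4% |
| B | 30/40/30% | 20/8/2% | 9.8% | 2.440 | 2.369 | 3.0% |
| C | 10/35/55% | 5/2/0.5% | 1.475% | 0.989 | 0.983 | 0.6% |

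Scenario A in full: P(1−P) = 0.04 × 0.96 = 0.0384. Within bands, 0.2 × 0.09 + 0.4 × 0.0384 + 0.4 × 0.0099 = 0.03732. Then √(0.0384/0.03732) = 1.014.

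A simulation of scenario B (20,000 trials, no true effect, near-balanced bands) gave a mean difference of −0.02 points for both the crude and the stratified estimate, which is Monte Carlo noise. Coverage of the 95% interval was 95.6% crude and 94.9% stratified. The crude interval is therefore slightly conservative, and the estimate is not biased.

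**Shift in the crude difference if only the regional arm loses infants (percentage points)**

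| Regional loss by band | A | B | C |
|---|---|---|---|
| 10/10/10% | 0 | 0 | 0 |
| 15/10/5% | 0.13 | 0.30 | 0.05 |
| 25/15/5% | 0.28 | 0.64 | 0.10 |
| 5/10/25% | −0.28 | −0.58 | −0.12 |
| 5/15/25% | −0.29 | −0.64 | −0.11 |

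Scenario B, second loss pattern: remaining shares are 0.225, 0.34 and 0.285, sum 0.85. The regional risk is (0.225 × 0.20 + 0.34 × 0.08 + 0.285 × 0.02)/0.85 = 0.0779/0.85 = 9.165%. The shift is 9.8 − 9.165 = 0.635 points. A stratified estimate has no shift in any of these rows.

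The non-zero shifts run from 0.05/0.989 = 5% to 0.635/2.440 = 26% of one standard error. The 25% end of the assumed losses matches the upper failure rate quoted in 1.4.4. Section 5.2.3 requires operators with success above 90%.

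**A second set of assumptions** gives the same order of size. Shares 20/40/40% with risks 10/3/0.3%: P = 0.0332, variance 0.03210 crude against 0.03084 within bands, a 3.9% reduction and an interval 2.0% narrower. Retention of 80/92/95% in the regional arm only moves its rate by −0.22 points. Shares 20/45/35% with risks 15/5/1% give 4.8%, 2.4% and −0.30 points; with risks 8/3/1% they give 2.0%, 1.0% and −0.15 points.

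**The case against.** **Silence is not the same as a crude analysis.** Section 8.2.1 never says the difference is unadjusted, and a stratified risk difference is also a difference in frequency. The estimator for a secondary binary outcome is often left to the SAP, which is not at hand. This stands as a limit on the point: the crude reading is an inference. It remains the natural one, because the same paragraph writes the adjustment into one sentence and leaves it out of the next.

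**Randomisation already deals with gestation.** A reader might infer that the frequency outcomes are open to confounding by prematurity. The documents do not support that. The confounding described in 1.4.2 works partly through choice of anaesthetic, which randomisation removes, and 3.2 also balances the bands. Bias needs loss or exclusion that depends on gestation differently in the two arms. The same gestation-dependent loss in both arms gives no shift when there is no true effect. Section 8.3 plans for 10% loss on average without splitting it by arm or gestation, and no per-protocol set is stated for frequency data. This objection stands in full.

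**The stated reason for adjusting is specific to IQ.** Section 8.3 refers to a common standard deviation, which does not carry over to a proportion. True, but it does not displace the general statement in 1.4.2.

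**Events may be sparse.** At a 0.3% risk in a term band holding 40% of infants, each arm expects 297 × 0.40 × 0.003 = 0.36 events, and the chance of none in either arm is about 50%. A logistic model with band terms could then fail through separation. This stands, and it shapes the fix.

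**Conclusion.** The point holds as a minor inconsistency. Section 8.2.1 does not carry the stratified analysis that 1.4.2 calls essential, and that 3.2 prepares for, through to binary neurodevelopmental outcomes.

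The cost of a crude analysis is an interval about 1% to 3% too wide (0.6% to 3.0% in scenarios A to C). If attrition or exclusion also differs by arm and gestation, there is a shift of about 0.05 to 0.64 percentage points against standard errors of about 1.0 to 2.4 points. All these sizes rest on assumed shares, risks and losses. No equivalence rule or other decision rule is attached to the frequency outcomes, so no trial conclusion turns on this.

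Two wider readings should be avoided. It is not the case that every continuous outcome is adjusted: section 8.2.3 names no adjustment, although time taken for nerve block and time to first feeding (6.2.3) are continuous. Nor does the protocol say that vision and hearing will be analysed as binary; only cerebral palsy is clearly so.

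**What to change.** In 8.2.1, replace the sentence on frequency data with a statement that these outcomes will be compared by a risk difference stratified by the three gestational-age bands used in randomisation, with Mantel-Haenszel weights and a matching 95% confidence interval suitable for sparse strata. This estimator remains defined when a band has no events in either arm, so it is preferable here to a logistic model with band terms. The same sentence should name the analysis population, since that decides whether the bias route above exists at all.

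The cost is one sentence and trivial programming. No new data are needed, and 598 and 660 are unchanged.

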8.2.3 Other outcomes related to anaesthesia group

All other outcomes related to anaesthesia group will be reported for each group with 2-sided 95% confidence interval.

8.2.4 Outcomes not related to anaesthesia group

These outcomes will be reported using descriptive statistics only.

8.3 Justification of numbers

The WPPSI-III full scale IQ score is a standardised score with a mean of 100 and standard deviation of 15. Cohort studies of ex-preterm babies at 5 years of age commonly show a mean of 95 and standard deviation of 15, while term babies have a mean of approximately 105 and a standard deviation of 15. A difference of 5 points (1/3 of a standard deviation) will be taken as the largest difference that would be acceptable to demonstrate equivalence.

The sample size is calculated using the two one-sided equivalence tests method (ref: Schuirmann, D.J.) with a one-sided alpha of 0.025, applied to the null hypothesis that the two methods of anaesthesia are not equivalent, and power of 90% under the alternative hypothesis that the true mean difference is one standardised score point. Restated, we require 90% probability that the 95% confidence interval for the difference in means, adjusted for gestational age at birth, will exclude a difference of 5 or more (i.e. the 95% CI will lie within the range -5 to +5), if the true difference is no more than one point. The trial then needs 598 infants in total. Enrolling 660 will allow for an average of 10% loss to follow-up.

Adjusting the analysis for gestational age at birth, according to the three categories used in the stratified randomization, will ensure that the common standard deviation assumption is protected from the differences in WPPSI-III full scale IQ mean scores between the gestational age groups. Simulations have been performed to confirm these calculations.

Reference

Schuirmann, D.J. A comparison of the two one-sided tests procedure and the power approach for assessing the equivalence of average bioavailability. Journal of Pharmacokinetics and Biopharmaceutics 15(1987) pp. 657-680

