1.4.4 Success rate and complication rate of general and regional anaesthesia

Regional anaesthesia has varying popularity. Proponents for regional anaesthesia claim that it results in a fast recovery, early feeding and low respiratory complication rate. Detractors of regional anaesthesia cite a substantial failure rate with regional anaesthesia (up to 25%) and potential for distress in the child as the block is performed. However, data supporting these comments are sparse and contradictory. This study will enable the collection of good quality data to help in answering these questions.

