4.5.3 Cancellation of surgery

If the surgery is cancelled after randomisation and not rescheduled, or cancelled and rescheduled greater than 48 hours after randomisation, then the reason for cancellation must be noted and the case is treated as a protocol violation. The child is not replaced. If the child has a hernia repair after 48 hours, the child should receive anaesthesia at the anaesthetist's discretion. Anaesthetic, apnoea and recovery data may be collected if possible. Note that as per other violations, the child should receive two and five year developmental assessment as per protocol. If the child receives surgery for hernia repair 48 hours or more after initial randomisation then they cannot be randomised again in the trial for that later surgery.

Note surgery may be *delayed for up to 48 hours* and the child retains their position in the study with same study group and study number (provided they continue to meet inclusion criteria).

If before anaesthesia and after randomisation a decision is made by surgeon or anaesthetist that the child is no longer suitable for the study for whatever reason (apart from cancelled surgery or withdrawn consent) and the child does not receive their allocated anaesthesia protocol, then the case should be treated as a protocol violation and data collected as possible. The child should receive the same post-anaesthesia apnoea data collection and developmental follow-up as per protocol. Note that if treating staff consider that it is in the child's best interests they always have the opportunity to not follow the protocol, but only the parents can withdraw the child completely from the trial.

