5.2.3 Experience of doctor performing nerve block

An essential component of the trial is a high success rate for regional anaesthesia. At each site awake spinal and caudal may be performed only by anaesthetists with an established high rate of success for the block (>90%). This anaesthetist may be called just to provide the block for the treating anaesthetist.

5.2.4 Asepsis: An aseptic technique is required for all blocks. This includes:

- Hands washed and sterile gloves worn
- Surgical masks to be worn
- Skin preparation with an antiseptic
- Area covered with sterile drapes

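### The 90% power in section 8.3 is worked out for infants followed up, but the primary analysis is per-protocol and 660 leaves no allowance for per-protocol exclusions

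*Protocol*

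**What the plan says.** **Analysis set.** Protocol section 8.1 states that "the primary outcome will be analysed on a perprotocol analysis basis", with the rule "Equivalence will be accepted if the confidence interval of the difference in means lies within -5 and +5 points".

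**Sample size.** Section 8.3 uses two one-sided tests "with a one-sided alpha of 0.025", a standard deviation of 15, a margin of 5 points and 90% power at a true difference of 1 point. It arrives at 598 infants. Enrolling 660 "will allow for an average of 10% loss to follow-up". No other allowance appears.

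**Departures that the protocol foresees.**
- Section 5.7: after a failed awake regional block the infant receives sevoflurane and stays in the study.
- Section 4.5.3: surgery cancelled, or rescheduled more than 48 hours after randomisation, is a protocol violation, as is a clinician's decision after randomisation not to give the allocated anaesthesia.
- Section 3.5.6.3: need for opioids or nitrous oxide is recorded as a violation, and management of a failed block is recorded under the same heading.

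**Replacement.** There is none. Section 4.5.3 says "The child is not replaced", and sections 4.5.1 and 4.5.2 say the same for their cases.

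**Block failure.** Section 5.2.3 restricts awake spinal and caudal blocks to anaesthetists with a success rate above 90%. Section 1.4.4 reports that critics of the technique cite failure of up to 25%, and adds that the supporting data are few and conflicting.

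**The concern.** The power statement and the primary analysis refer to different sets of infants. Section 8.3 counts everyone who returns at 5 years. Section 8.1 tests equivalence on those who return and were also treated as the protocol requires. The second set cannot be larger and will be smaller if any followed-up infant is excluded for a violation. Conversions would fall on the regional arm only, so they also unbalance the comparison.

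At stake is the chance of a conclusive result. With fewer infants the confidence interval widens, and an interval that crosses a margin becomes likelier than the 10% that the protocol accepts at its design difference.

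**Working it through.** **Inputs.** Margin 5, SD 15, true difference 1, one-sided alpha 0.025, 598 needed, 660 enrolled, 10% loss (sections 8.1 and 8.3). The allocation ratio is not stated; 1:1 is assumed, giving 330 per arm. Excluding converted infants from the per-protocol set is also an assumption.

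**Formula.** With SE = 15 × √(1/n₁ + 1/n₂), the normal approximation to the power of the two one-sided tests is

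Φ((5 − 1)/SE − 1.96) − Φ(−(5 + 1)/SE + 1.96).

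The exact version uses the t distribution and is about 0.1 point lower.

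**Step 1: reproduce the plan.** At 299 per arm, SE = 15 × √(2/299) = 1.227. Power = Φ(1.301) − Φ(−2.931) = 0.9033 − 0.0017 = 90.2%; the exact value is 90.07%. At 298 per arm the exact value is 89.97%. So 598 is confirmed.

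**Step 2: apply the planned loss.** 660 × 0.9 = 594, or 297 per arm. SE = 1.231 and exact power is 89.87%. The planned loss consumes the whole allowance.

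**Step 3: remove converted infants from the regional arm.** The general arm stays at 297 and the regional arm is 297 × (1 − conversion rate).

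| Conversion | General v regional | Total | SE | Power, normal | Power, exact |
|---|---|---|---|---|---|
| 0% | 297 v 297 | 594 | 1.231 | 90.0% | 89.9% |
| 5% | 297 v 282 | 579 | 1.247 | 89.2% | 89.1% |
| 10% (limit implied by 5.2.3) | 297 v 267 | 564 | 1.265 | 88.3% | 88.2% |
| 25% (sensitivity, 1.4.4) | 297 v 223 | 520 | 1.329 | 84.8% | 84.6% |

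**Step 4: read the result.** The chance of an inconclusive interval at a true difference of 1 point rises from about 10% to about 12% at 10% conversion, and to about 15% in the sensitivity case.

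**Step 5: other violations.** Rescheduling beyond 48 hours, or opioid or nitrous oxide use, would lower these figures further if they lead to exclusion. The documents project no rate for them, so no figure is given here.

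**The case against.** **Membership of the set is inferred.** The protocol does not define the per-protocol set; that may be left to an analysis plan that is not at hand, and section 5.7 keeps converted infants in the study. This stands as a caveat. Even so, section 4.5.3 requires violators to have the 2- and 5-year assessments, so staying in the study does not imply membership of the set. Section 8.1 chose per-protocol to be conservative towards non-equivalence. Keeping sevoflurane-exposed infants in the regional arm would work against that aim.

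**The loss of power is small and conditional.** This stands. At the success rate that section 5.2.3 demands, it is about 1 to 2 points. If follow-up loss were 5% instead of 10%, power at 10% conversion would be about 89.8% (313 v 282). At a true difference of zero, power would be 95.3% at 10% conversion and 92.7% at 25%. The protocol's claim, however, is made at 1 point and 10% loss.

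**Stronger readings that the documents do not support.**
- A reader might infer that 660 fails even for loss alone, since 598/0.9 = 665. The gap between 594 and 598 is worth 0.2 points of power, and 660 covers a loss of 9.4% in full (1 − 598/660) against a planned average of 10%. That is rounding.
- A reader might take 25% as the trial's expected failure rate. Section 1.4.4 attributes it to critics and discounts the evidence. Section 5.2.3 sets a stricter condition, and section 5.7 permits a second spinal attempt after total failure.
- A reader might want a fixed size for the per-protocol set. The protocol projects no exclusion rates, so any size depends on assumed ones.

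**Conclusion.** The point holds as a mismatch between sections 8.1 and 8.3, and it is moderate in weight. The stated 90% belongs to the followed-up infants, not to the set on which equivalence will be judged. At the planned 10% loss nothing is left to absorb exclusions. Power on the per-protocol set is about 89% at 5% conversion and 88% at 10%, and 84.6% in the 25% sensitivity case.

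These figures rest on 1:1 allocation, SD 15, a true difference of 1 point, 10% loss in each arm and exclusion of converted infants. The figures 598 and 660 are sound for loss to follow-up alone. The missing allowance does not affect type I error, the margin or the validity of the interval. What is overstated is the chance of a conclusive answer.

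**What to change.** Keep 660 and restate section 8.3 for the per-protocol set:
- the assumed loss to follow-up (10%);
- the assumed conversion rate in the regional arm, and whether converted infants leave the set;
- the assumed rate of other exclusions;
- the resulting per-protocol numbers in each arm;
- the resulting power, about 88% at 10% conversion before any other exclusions, with a higher conversion rate shown as a sensitivity case.

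Section 7.2 already has the DMC consider the rate of conversion to general anaesthesia. Add that it compares this rate with the one assumed in section 8.3.

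The cost is protocol wording and a slightly less favourable power statement. No extra infants are needed and clinical care does not change.

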3.5.4 Medical and social history

The following medical and social history data will be collected:

Language spoken at home Family structure with details of parents including who is primary income earner, who is primary carer and details of employment status and education Maternal age at birth of child Presence in family of anyone with a mental or learning disorder Gender Method of calculating expected date of delivery Birth weight, in kg Apgar score at 1 and 5 minutes, mode of delivery, if the child was part of a multiple pregnancy, presence of labour, antenatal steroids, history of prolonged rupture of membranes, pre-eclampsia or chorioamnionitis History and details of previous apnoea or respiratory support Details of any previous neurological injury or intraventricular haemorrhage Previous ROP or hearing defects Previous sepsis Days the child spent in hospital after birth and date child last discharged from hospital

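### The primary IQ analysis names gestational age as its only covariate; a short, locked list of baseline predictors already collected would be a cheap gain in precision

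*Protocol*

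**What the plan says.** Section 8.1 makes the primary analysis of WPPSI-III Full Scale IQ per-protocol and states: "The means will be adjusted for gestational age at birth". The decision rule there is: "Equivalence will be accepted if the confidence interval of the difference in means lies within -5 and +5 points".

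Section 8.3 makes the adjustment specific: "Adjusting the analysis for gestational age at birth, according to the three categories used in the stratified randomization". The reason given is to keep differences in mean IQ between gestational groups out of the common standard deviation. No other covariate is named in either section.

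Section 3.5.4 lists what is recorded on medical and social history. It includes maternal age, birth weight, parental details ("who is primary carer and details of employment status and education") and, as two list items run together in the text, "Presence in family of anyone with a mental or learning disorder Gender". The protocol does not say how strongly any of these relate to IQ.

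**The concern.** Equivalence is decided by whether a 95% interval fits inside plus or minus 5 points, so its width matters directly. Baseline variables that predict IQ beyond gestational band would reduce residual variance and narrow that interval, without enrolling or measuring anyone further. As written, 8.1 leaves this unused.

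Two features of the plan make it more relevant. The 10% enrolment allowance in 8.3 covers loss to follow-up only, so there is no reserve for infants left out of a per-protocol set. And any exclusions for failed awake regional anaesthesia fall after randomisation and in one arm, so balance on family and birth factors is no longer guaranteed by design.

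**Working it through.** **Inputs from the protocol.** Margin 5 points (8.1). SD 15; 8.3 quotes it for ex-preterm children ("Cohort studies of ex-preterm babies at 5 years of age commonly show a mean of 95 and standard deviation of 15") and again for term children, so it is already a within-gestation SD. Test level: "with a one-sided alpha of 0.025, applied to the null hypothesis that the two methods of anaesthesia are not equivalent". Target: "power of 90% under the alternative hypothesis that the true mean difference is one standardised score point". Evaluable 598, enrolled 660, 10% loss (8.3). Regional failure is cited at up to 25% (1.4.4), and awake blocks are restricted to anaesthetists with success above 90% (5.2.3).

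**Assumptions.** 1:1 allocation. R2, the share of within-stratum IQ variance explained by the extra covariates, is 0.05 to 0.20. Failed regional cases are excluded from the primary set, at 10% or 25% of the regional arm.

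**Formulas.** SE = 15 × √(1 − R2) × √(1/n1 + 1/n2). Power, normal form = Φ((5 − 1)/SE − 1.96) − Φ((−5 − 1)/SE + 1.96). The results below use the noncentral t version of the same two one-sided tests, which runs about 0.1 point lower.

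**Step 1: the plan's own figure.** At 299 per arm, SE = 15 × √(2/299) = 1.227. The normal form gives Φ(1.30) − Φ(−2.93), or 90.2%. Noncentral t gives 90.07% at 299 per arm and 89.97% at 298, so 299 is the first size above 90%. That is 598 in total, as stated.

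**Step 2: evaluable numbers.** 660 × 0.9 = 594, or 297 per arm. With 10% of the regional arm excluded, 297 × 0.90 = 267. With 25% excluded, 297 × 0.75 = 223.

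**Step 3: gain in precision.** The SE is multiplied by √(1 − R2), and the equivalent gain in sample size is 1/(1 − R2) − 1.

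- R2 = 0.05: SE falls 2.5%, worth 5% more infants.
- R2 = 0.10: SE falls 5.1%, worth 11% more.
- R2 = 0.20: SE falls 10.6%, worth 25% more.

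**Step 4: power, with SE in brackets.**

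| Evaluable, general v regional | Gestation only | R2 = 0.05 | R2 = 0.10 | R2 = 0.20 |
|---|---|---|---|---|
| 297 v 297 | 89.9% (1.231) | 91.3% (1.200) | 92.7% (1.168) | 95.2% (1.101) |
| 297 v 267 | 88.2% (1.265) | 89.8% (1.233) | 91.3% (1.200) | 94.1% (1.131) |
| 297 v 223 | 84.6% (1.329) | 86.5% (1.295) | 88.4% (1.261) | 91.8% (1.189) |

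**Step 5: break-even.** The R2 needed to return to 90% is 5.4% at 10% conversion and 14.4% at 25% by the normal form (5.8% and 14.7% by noncentral t). If both arms also lost 10% to other violations, with 25% conversion, power would be 80.4% and the R2 needed about 23% (normal form).

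**The case against.** The strongest case against is that nothing here is wrong. Adjusting for a stratification factor is legitimate, 8.3 gives a coherent reason for it, and the one predictor whose effect on IQ the protocol quantifies (means of 95 and about 105 by gestation) is already in the model. Further covariates may be set out in an analysis plan that is not at hand. All of this stands, and it limits the point to an improvement. It does not remove it, because 8.1 and 8.3 state a specific adjustment and a longer list would depart from that wording.

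The power loss is also partly inferred. The per-protocol set is not defined, and 5.7 says that a failed regional case continues in the study. Section 1.4.4 attributes the 25% to detractors of the technique and calls the supporting data sparse and contradictory. At 10% conversion the loss is under 2 points. This stands too, so the exclusion rows are scenarios.

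A reader might infer that adjustment would repair the bias from a per-protocol primary analysis. The documents do not support that. The failure causes given in 5.7 and 7.3.1 (movement, inconsolable crying, technical failure, a block insufficient for the surgery) are not linked there to the family or birth variables. Adjustment can reduce imbalance on what is measured; it cannot remove selection from excluding failures in one arm.

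Finally, the choice of variables is open to debate. Birth weight overlaps with gestational age, education is recorded under different school systems, and site, the other stratification factor, has its own claim to enter the model. These are reasons to treat the list below as illustrative.

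**Conclusion.** The point holds as a modest, low-cost gain in precision. The gestation-only model is valid and 598 is the right number for it. At 594 evaluable infants the gain is 1.4 to 5.3 points of power (91.3% − 89.9% and 95.2% − 89.9%) for an assumed R2 of 0.05 to 0.20. If failed blocks are excluded, the added covariates offset the loss in part or in full. At 10% conversion, an R2 of 0.05 falls just short of 90% and 0.10 exceeds it. At 25% conversion, 0.10 still falls short and 0.20 exceeds it.

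It would be tempting to call these variables strong predictors whose omission costs the trial its power, or to say that adding them would restore it. The protocol supports neither: it gives no R2 or correlation for any of them, and recovery depends on both that unknown figure and an exclusion rate that the document does not fix.

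**What to change.** In 8.1, state that the mean difference in Full Scale IQ is adjusted for gestational-age stratum plus a short fixed list of baseline variables already collected, for example sex, primary carer's education in harmonised categories, maternal age and birth weight. Lock the list and the coding of each variable before any 5-year data are unblinded. Report the gestation-only model as a supporting analysis, and bring the wording in 8.3 into line. The sample size need not change. If an analysis plan already specifies such a list, aligning 8.1 with it is enough.

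The cost is protocol wording, agreement on education categories that work across the participating countries, and a simple imputation rule for the few baseline values likely to be missing.
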